## **3.0 Subject Selection and Enrollment**

3.1 Subjects: Twenty adult healthy volunteers will be recruited for this study. They will be solicited from within the University of Michigan Health System (e.g. students, staff, and employees). No financial incentive will be provided.

3.2 Inclusion Criteria:

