## **4.0 Study Procedures**

4.1 Written informed consent will be obtained on all subjects prior to enrollment in the study and before any research procedures are performed. Subjects can withdraw from the study at any time.

4.2 Subjects will undergo testing by applying NPPV via 2 different BiPAP devices that are currently used in standard of care for patients at the University of Michigan Health System. The decision of which device to begin with will be determined by random allocation of a coin toss.

4.3 BiPAP Systems:

4.3.1 The Resironics V-60 (Phillips, Carlsbad CA) device is continuous high flow, blower type of generator.

4.3.2 The Drager V-500 (Drager Medical, Lubeck, Germany) is our primary critical care ventilator that has a specific NPPV mode.

- 4.4 EIT System: The Drager PulmoVista 500 EIT system (Drager Medical, Lubeck, Germany) consists of an electrode belt connected to the EIT monitor. Before using the system it will be reviewed and approved for use by our Biomedical Department.
- 4.5 Subjects will be placed in the supine position. This position will be maintained for the entire procedure. An electrode belt will be placed on the subject at the 5th intercostal space and connected to the EIT monitor. Prior to initiating a study session, the EIT system will be calibrated per manufacturer's instruction.
- 4.6 Each study device will be applied in the following manner:
  - 4.6.1 Four steps (series of device setting changes) will be applied, as such:
    - 4.6.1.1 A baseline will be established breathing without the NPPV mask attached
    - 4.6.1.2 Following mask attachment, a pressure support of 0 cm H2O and PEEP of 5 cm H2O will be applied, then
    - 4.6.1.3 A pressure support of 5 cm H2O and PEEP of 5 cm H2O, then
    - 4.6.1.4 A pressure support of 5 cm H2O and PEEP of 10 cm H2O.
  - 4.6.2 Each step will consist of a 5-minute stabilization period, and then readings will be taken over the next two minutes before proceeding to the next step.
  - 4.6.3 Following all four steps with the initial device, the second device will be applied and steps 1-4 repeated.
- 4.7 Primary Outcomes: Global Tidal Variation (see figures 4-6)
- 4.8 Secondary Outcomes:
  - 4.8.1 Regional Tidal Variations
  - 4.8.2 Global and Regional changes in End-Expiratory Lung Impedance (EELI)
- 4.9 Exploratory Outcomes:

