  - 4.9.1 A pneumotachometer (NM3 monitor, Phillips Healthcare, Andover MA), will be placed between the mask and inspiratory hose and the following measurements obtained: respiratory rate, tidal volume, peak inspiratory

pressure, PEEP. A pulse oximeter (RAD8, Masimo, Irvine CA) will provide SpO2 and heart rate.

- 4.9.2 Change in regional and global distribution in subjects with a BMI less than or greater than 25 kg/m^2
- 4.9.3 Change in global and regional distribution for subjects at 0 degrees, 45 degrees, and 90 degrees' body positions.

4.10 In addition to device testing, baseline demographics such as age and gender will be recorded for each subject.

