## 5.0 Statistical Analysis

A two-way ANOVA will be the first step of analysis to determine the influence of the BiPAP systems on the NPPV. Regional distribution of tidal volume will be analyzed using four ventral to dorsal regions of interest (ROI) by EIT. The relative distribution of tidal volume between regions will be displayed as a percentage. Regional change in end-expiratory lung impedance (EELI) will be similarly expressed as a percent for each ROI. These parameters will be treated as functions of each individual step outlined in 4.6, with particular attention paid to the pressure support and PEEP. Values will be presented as mean  $\pm$  standard deviation and initial comparisons will be made using paired *t*-tests against baseline. Given the factorial design of experiment, if further analysis becomes warranted, a multivariate ANOVA will be utilized to determine the time, pressure, and total tidal volume relationship to relative distribution of tidal volume within the regions of interest. Potential confounding parameters such as patient size, weight, and health status will be screened in a similar manner.

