Figure 4. Main Screen

This screen depicts: 1) on the left: Dynamic Image (showing impedance changes over time) and Status Image (image used to derive waveforms and percentages) of the lungs, 2) in the center: a global impedance wave form at the top and 4 regional impedance waveforms (one for each ROI) and 3) on the right: the Tidal Rate, the global Tidal Variation (100%) and the regional Tidal variation percentages for each ROI

[figure not shown]

Figure 5. Trend View

Two status images are displayed (baseline and following an intervention) to graphically represent regional ventilation distribution over a time period of up to 120 minutes.

[figure not shown]

Figure 6. Delta EELV Trend View

Figure shows waveforms of the global (top center) and four regional changes in end-expiratory lung impedance. Corresponding numeric values are shown on the right.

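### If all four ROI percentages enter the fallback MANOVA, the response is singular; the plan should specify three log-ratios (or three shares) in a model with a subject effect, and say which tidal volume is meant

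*Combined protocol and SAP*

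**What the plan says.** Section 5.0 sets the regional outcome: "Regional distribution of tidal volume will be analyzed using four ventral to dorsal regions of interest (ROI) by EIT", and "The relative distribution of tidal volume between regions will be displayed as a percentage". The caption to Figure 4 describes what the monitor displays: "the global Tidal Variation (100%) and the regional Tidal variation percentages for each ROI". So the global value is 100% and the regions divide it.

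After a two-way ANOVA and paired t-tests against baseline, section 5.0 adds a step to be used only if more analysis is judged necessary: "a multivariate ANOVA will be utilized to determine the time, pressure, and total tidal volume relationship to relative distribution of tidal volume". It does not say which shares form the response vector, whether one is omitted or a transformation is used, which measure total tidal volume refers to, or how the eight readings per subject are handled.

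On measurement, section 4.6.1.1 says "A baseline will be established breathing without the NPPV mask attached". Section 4.9.1 lists a pneumotachometer that "will be placed between the mask and inspiratory hose" as the source of tidal volume. Section 4.6.3 repeats all four steps, baseline included, with the second device. On size, section 3.1 says "Twenty adult healthy volunteers will be recruited for this study".

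**The concern.** A MANOVA inverts the error covariance matrix of its responses. When the responses are all the parts of a fixed total, one is an exact linear function of the others and no inverse exists. Software does not reliably stop and say so. It may report an error, or return a p-value on the wrong degrees of freedom. If the shares were exported as whole percentages, it may run cleanly with rounding error as the fourth response.

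The tidal-volume term raises a second question. A sensor in the mask circuit has nothing to measure when the mask is off. If that sensor supplies the covariate, the baseline rows leave the model without comment, and with them the contrast between unassisted breathing and each pressure step.

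At stake is the one named model that relates tidal volume to regional distribution, on a secondary outcome (4.8.1).

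**Working it through.** The plan states no alpha, power, effect size or SD, so it has no figure to reproduce. Assumed throughout: two-sided alpha 0.05 and the effects and SDs given below.

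**1. Rank.** With shares p1 + p2 + p3 + p4 = 100 in every reading, the residuals in each row sum to 0, so the error matrix E satisfies E·(1,1,1,1)' = 0 and has rank at most 3.
- 160 simulated exact shares: eigenvalues about 2e-15, 17.3, 26.4 and 28.4.
- The same shares rounded to whole percent (rounding is an assumption): 0.08, 17.3, 26.4 and 28.5. The matrix is now invertible, but the smallest dimension is only rounding error.

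**2. What software does.** One MANOVA run on four exact simulated shares printed a Wilks test on 12 df (4 responses × 3), p = 0.34. The valid test has 9 df (3 × 3), p = 0.14. In simulated paired comparisons with n = 20 (log-scale SD 0.12 in the run with the most detail), four exact shares failed in 6% to 8% of runs and rejected a true null in about 2% of the rest, against a nominal 5%. Four rounded shares rejected in about 5%, so rounding costs power and not validity.

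**3. Size of the power loss.** For a paired contrast with n = 20, Hotelling's test on k responses uses F(k, 20 − k) with noncentrality 20·D², where D is the standardised (Mahalanobis) shift. A rounding dimension raises k from 3 to 4 and leaves D unchanged. A single dorsal share uses a t-test on 19 df with noncentrality d·√20. With the whole shift along the dorsal contrast (D = d):

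| d | four rounded shares | three shares | dorsal share |
|---|---|---|---|
| 0.4 | 20.2% | 23.8% | 39.7% |
| 0.5 | 30.3% | 35.8% | 56.5% |
| 0.6 | 42.8% | 49.8% | 72.1% |
| 0.8 | 69.5% | 76.8% | 92.4% |

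Simulation agrees: at a shift of 0.05 log units, power was about 41% for four rounded shares, 48% for three shares and 65% to 69% for the dorsal share.

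**4. When the shift is not along the dorsal contrast.** Assume an SD of change of 3 points per ROI with equal covariances of −3. The dorsal sum then has variance 9 + 9 − 6 = 12, so d = (m3 + m4)/√12 and D² = Σm²/12.

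| Mean shift, ROI 1 to 4 (points) | d | D² | dorsal share | three shares |
|---|---|---|---|---|
| −2, −1, +1, +2 | 0.87 | 0.83 | 95.6% | 87.6% |
| −2, 0, 0, +2 | 0.58 | 0.67 | 68.8% | 78.7% |
| −3, +1.5, 0, +1.5 | 0.43 | 1.13 | 45.2% | 95.6% |
| −2, +2, +2, −2 | 0 | 1.33 | 5.0% | 98.1% |

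**5. Repair.** On one simulated data set, omitting ROI 1, 2, 3 or 4 in turn gave T² = 10.2846 each time. The choice of omitted share does not change the joint test.

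**6. Tidal volume.** Records: 20 subjects × 2 devices × 4 steps = 160. Off-mask baseline: 20 × 2 × 1 = 40. Remaining: 160 − 40 = 120.

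**The case against.** The strongest reply is that this is a small matter. The MANOVA runs only if judged necessary, on a secondary outcome; the primary is Global Tidal Variation (4.7). The text does not state that all four shares are entered, and a careful analyst would omit one and get the same answer whichever it was. Total tidal volume may mean the EIT global signal, since section 5.0 uses tidal volume for the EIT quantity elsewhere, and that signal exists off the mask.

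Most of this stands and sets the limits of the point. What remains is that the plan leaves the repair to chance, and the output in step 2 shows that a wrong p-value can appear without a failure. The EIT reading also needs stating: the displayed global value is 100% and constant, so only impedance units could serve as a predictor.

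Three stronger readings are tempting and not supported:
- *The model cannot be fitted.* The singularity arises only if all four shares are entered, and missing baseline tidal volumes remove rows without blocking the fit.
- *The MANOVA is the only test of the ventral-to-dorsal hypothesis.* Section 5.0 already examines the regional measures by step and uses paired t-tests against baseline. Tests on one share at a time are untouched by the sum constraint, and the hypothesis in section 2.0 does not mention tidal volume.
- *A single dorsal share is always the stronger analysis.* The second table shows the order reversing, and the documents give no covariances to settle which pattern applies.

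**Conclusion.** The point holds in a limited form. If all four percentages are entered, which is the natural reading, the four-response MANOVA is not validly defined: rank 3 of 4, whatever the data. With exact shares the result is an occasional failure or a distorted test. With rounded shares it is a loss of about 4 to 7 points of power over d = 0.4 to 0.8. If the pneumotachometer supplies total tidal volume, a quarter of the records (40 of 160) and the baseline contrast are lost.

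The rank result and the record count follow from the documents, the latter under that reading of tidal volume. Every power figure rests on assumed alpha, effects and SDs, and on a paired two-condition comparison, not the full planned model. Because this is a conditional fallback on a secondary outcome, it merits correction but does not threaten the primary analysis.

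**What to change.** Amend section 5.0 as follows.
- Replace the four-percentage MANOVA with a repeated-measures or mixed model with a subject effect, on three log-ratios of the four shares (or on three of the four shares). Fixed effects: device, step, device × step and period.
- Name the tidal-volume measure. Use EIT global tidal variation in impedance units when baseline is included, and pneumotachometer tidal volume only in an analysis of the mask-on steps.
- Optionally add a pre-specified dorsal share (ROI 3 + ROI 4) as a direct test of the hypothesised shift, noting that it gains power only if the shift lies along that contrast.

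The cost is SAP wording; no new data are needed. The mask-on analysis still uses only 120 records, and the dorsal share misses movement between ROI 3 and ROI 4, so it should accompany the joint regional analysis, not replace it. Because the steps run in a fixed order, the step effect carries pressure and elapsed time together. The amended text should say so and not promise separate effects.

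### Section 5.0 screens fixed subject traits as confounders, but with complete data they cannot bias the device or pressure contrasts, and testing them on condition-level rows would over-flag them (minor)

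*Combined protocol and SAP*

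**What the plan says.** - **Design (3.1, 4.2, 4.6).** "Twenty adult healthy volunteers will be recruited for this study". "Subjects will undergo testing by applying NPPV via 2 different BiPAP devices", and the starting device is randomised: "The decision of which device to begin with will be determined by random allocation of a coin toss". Each device is taken through a baseline without the mask and three pressure settings, and 4.6.3 adds: "Following all four steps with the initial device, the second device will be applied and steps 1-4 repeated".
- **Main analysis (5.0).** "A two-way ANOVA will be the first step of analysis to determine the influence of the BiPAP systems on the NPPV". Paired t-tests against baseline are also planned. If more analysis is judged necessary, a multivariate ANOVA will relate regional shares to time, pressure and overall tidal volume. No subject or repeated-measures term is named for either ANOVA.
- **Trait screen (5.0, last sentence).** "Potential confounding parameters such as patient size, weight, and health status will be screened in a similar manner". The unit of analysis, significance level, flagging threshold and consequence of a flag are not given.
- **Trait data (4.9.2, 4.10).** A comparison of subjects below and above a BMI of 25 is listed as exploratory. Section 4.10 says that "baseline demographics such as age and gender will be recorded for each subject"; weight and height are not named there, although BMI requires both.

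**The concern.** A confounder of a contrast must differ between the conditions being compared. In this crossover, size, weight and health status do not: the same person sits on both sides of each device and pressure comparison. For the hypotheses in 2.0 these traits can be effect modifiers (the device difference may vary with body size), and a main-effect screen does not address that.

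The second issue is how the screen would be run. Its wording points back to a model with predictors that change during a session, so the natural data layout is one row per subject per condition. A trait has at most 20 distinct values however many rows carry it. If the rows are treated as independent, its standard error is too small and irrelevant traits are flagged too often. At stake is a published statement that, say, weight influences ventilation distribution when the data show no such thing.

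**Working it through.** The documents state no significance level, power or error rate for this screen, so there is no planned figure to reproduce.

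**Inputs.** From the documents: 20 subjects (3.1), 2 devices (4.2) and 4 steps per device (4.6.1). That gives m = 2 × 4 = 8 rows per subject and 20 × 8 = 160 rows. Without the two mask-off baselines, m = 6 and there are 120 rows. Assumed: two-sided 5% level and ICC between 0.1 and 0.8.

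**1. Can a trait bias the device or step contrast?** In one simulated complete data set (20 subjects, 8 rows each) the trait was correlated with the outcome. The device estimate was 0.4146 with and without the trait in the model, and the step estimate was 1.2904 both ways. A fixed trait is balanced across conditions, so it drops out.

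**2. False flags on condition-level rows.** Treating m correlated rows as independent understates the variance of a subject-level slope by D = 1 + (m − 1) × ICC. The false-positive rate for one null trait and one outcome is 2 × [1 − Φ(1.96/√D)]. For example, with m = 8 and ICC 0.5, D = 1 + 7 × 0.5 = 4.5 and 1.96/√4.5 = 0.924, giving 35.6%. For a row-level MANOVA on the three free components of the four regional percentages (assumed independent, with equal ICC), the rate is P(χ²₃ > 7.81/D). Simulations used 1,500 runs per cell with condition terms in the model.

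| Rows per subject | ICC | D | Univariate, formula | Univariate, simulated | Row-level MANOVA, formula | One mean per subject, simulated |
|---|---|---|---|---|---|---|
| 8 | 0.1 | 1.7 | 13.3% | 13.5% | 20.4% | 4.5% |
| 8 | 0.3 | 3.1 | 26.6% | 24.2% | 47.2% | 3.9% |
| 8 | 0.5 | 4.5 | 35.6% | 37.0% | 62.9% | 5.3% |
| 8 | 0.8 | 6.6 | 44.6% | 45.2% | 75.7% | 5.9% |
| 6 | 0.1 | 1.5 | 11.0% | 9.7% | 15.7% | 4.2% |
| 6 | 0.3 | 2.5 | 21.5% | 22.7% | 37.3% | 4.8% |
| 6 | 0.5 | 3.5 | 29.5% | 29.8% | 52.6% | 4.5% |
| 6 | 0.8 | 5.0 | 38.1% | 40.5% | 66.8% | 4.3% |

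**3. Where a trait can still matter.** Two illustrations with invented effect sizes:

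- *Tidal-volume slope.* Size drives both tidal volume (slope 1, residual SD 0.7) and the outcome (slope 0.5), and the true tidal-volume effect is 0. The expected pooled slope is 0.5/(1 + 0.7²) = 0.5/1.49 = 0.34. Simulation gave 0.32 without size, 0.00 with size, and 0.00 within subject with no trait in the model.
- *Incomplete sessions.* Subjects more than 1 SD above mean size lack second-device data and no subject effect is fitted. Device bias was −0.29 without size and 0.00 with it.

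**The case against.** The strongest reply is that the screen does have a target. The sentence follows a model that includes tidal volume, which is observed rather than assigned and differs between subjects as well as within them. Body size can confound that relationship, and the first illustration shows it. Incomplete sessions are also possible, since 4.1 allows withdrawal at any time. This stands: a reader might infer that the screen can never remove bias and should simply be deleted, and section 5.0 does not support that. In the tidal-volume illustration, however, the within-subject slope is already unbiased without any trait. A subject effect likewise absorbs any additive fixed trait when sessions are incomplete, including traits nobody measured.

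A second reply is that the plan does not say the screen uses condition-level rows. That is also correct. A repeated-measures analysis with one row per subject would not show the inflation, and the planned t-tests are paired. The rates are therefore conditional on one permitted reading; they are not a property of the plan.

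Third, the consequences are limited. The multivariate ANOVA is itself conditional, no trait-adjusted device analysis is announced, and 4.9.2 already looks at BMI. All of this stands and lowers the severity.

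Finally, a reader might multiply up to the chance that at least one of three traits is flagged. With 8 rows and ICC 0.3 to 0.8, simulation gives 59% to 83%, but only for mutually independent traits. Size and weight are related, and health status may hardly vary among healthy volunteers, so that figure should not be used.

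**Conclusion.** The point holds in a limited form and is minor. With complete data, size, weight and health status cannot confound the device or pressure-step contrasts in 2.0, so the label in 5.0 is wrong for those contrasts. If the screen is run on subject-by-condition rows treated as independent, one irrelevant trait is flagged several times more often than the nominal rate: about 27% to 45% with 8 rows and 22% to 38% with 6 rows at ICC 0.3 to 0.8, and still 11% to 13% at ICC 0.1. A row-level MANOVA would do worse. These figures rest on an assumed 5% level, an assumed ICC and an inferred row structure.

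A reader might infer that the device comparison itself is compromised. It is not: with complete data, adding a falsely flagged trait leaves the device estimate unchanged. What is at risk is a spurious secondary statement about a trait.

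**What to change.** Replace the last sentence of 5.0 with:

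> All ANOVA and MANOVA models will include a subject effect, so that the device, pressure and tidal-volume relationships are estimated within subject. Size and weight will be examined as possible effect modifiers, not confounders, of the device and pressure comparisons: each subject's device difference and each subject's change in dorsal share across the mask-on steps (one value per subject, n = 20) will be regressed on each trait and reported as exploratory slopes with 95% confidence intervals, alongside the BMI comparison in 4.9.2. Health status will be described only, as all subjects are healthy volunteers.

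Two details need settling. For the tidal-volume slope to be strictly within subject, enter subject as a fixed factor or centre tidal volume on each subject's mean. Define size and add it, with weight, to the list in 4.10.

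The cost is a few sentences and no new measurements beyond those BMI already requires. Intervals for trait effects will be wider, because they reflect 20 subjects rather than 160 rows. The slopes should stay descriptive: even at subject level, three independent null traits each tested at 5% give a 13% to 16% chance of at least one flag (simulated).

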## 6.0 Risks

The total procedure should be completed within 90-120 minutes. There is minimal risk or discomfort to the subject. The electrode belt will not be applied long enough for any chafing or skin breakdown to occur. Although hyperventilation (i.e. lightheadedness, tingling in the hands) may occur as airway pressure is applied, the subject will be monitored continuously and the pressures used are relatively low compared to those used clinically or at home for sleep apnea.

## 7.0 Benefits

There will be no direct benefit to the study subjects. This research will 1) provide an opportunity to learn the EIT system in a nonclinical application on healthy volunteers

before using it in a clinical protocol, and 2) allow comparison of NPPV systems that are routinely used clinically to hopefully show equivalence in important measures.

## **8.0 Safety Monitoring/Reporting**

8.1 Due to the minimal risk of this study, only related adverse events will be reported.

- 8.1.1 Serious, related adverse events will be reported to the IRB within 7 calendar days
- 8.1.2 Non-serious, related adverse events grade 3 or higher will be reported to the IRB prior to SCR
- 8.1.3 Any serious, unanticipated problems that are related to the study and indicate risks to subjects will be reported to the IRB within 7 calendar days. Non-serious problems will be reported within 14 days.
- 8.1.4 Privacy violation or breach of confidentiality will be reported to the IRB within 7 calendar days, and to the UMHS Privacy Office within 24 hours.

